11. SAFETY ANALYSIS

All analyses of safety data will be conducted using the safety population unless otherwise specified. Safety summaries based on the safety population will be provided by treatment and pre-specified CCR option (Overall, BSC only, Azacitidine + BSC, LDAC + BSC, IDAC + BSC). Dosing summaries will be carried out for each study drug separately.

For summaries of safety data, the treatment period is defined as follows:

- AG-221, azacitidine, LDAC and IDAC AZA: date of first dose through date of last dose + 28 days, or until the EOT visit, whichever is longer;
- BSC only: date of randomization through date of treatment discontinuation.

11.1. Adverse Events

Adverse events will be analyzed in terms of treatment-emergent adverse events (TEAEs) which are defined as any AEs that begin or worsen on or after the start of study drug through 28 days after the last study treatment or until the EOT visit, whichever is longer, as well as those serious adverse events (SAEs) made known to the Investigator at any time thereafter that are suspected of being related to investigational product. All AEs will be coded using the Medical Dictionary for Regulatory Affairs® (MedDRA) version 22.0. The severity will be graded by the study personnel based on NCI National Cancer Institute Common Terminology Criteria for Adverse Events (CTCAE) Version 4.03.

A treatment-related TEAE is defined as TEAE that is suspected by the Investigator to be related to study treatment.

If a subject experiences the same AE more than once with different toxicity grade, then the event with the highest grade will be tabulated in “by grade” tables. If a subject experiences multiple AEs under the same preferred term (system organ class), then the subject will be counted only once for that preferred term (system organ class).

Summarizations of TEAEs per person-year of exposure are carried out in exposure-adjusted event rate, which is defined as number of events occurred in treatment exposure duration.

The number of subjects with at least one TEAE will be summarized. The incidence of TEAEs will be summarized by alphabetic order of SOC and descending order of PT for AG-221 group. Tables summarizing the incidence of TEAEs will be generated for each of the following:

- Summary of TEAEs;
- All TEAEs by SOC and PT;
- All TEAEs by decreasing frequency of PT for AG-221;
- All TEAEs per person-year of exposure, person-years of exposure is defined as (Sum of subjects’ overall treatment exposure (days) from first dose date (or randomization date for BSC only group) to the end of the TEAE period [c])/365.25;
- TEAEs related to study treatment;
- TEAEs by maximum severity;

- TEAEs with CTCAE grade ≥ 3 ;
- Related TEAEs with CTCAE grade ≥ 3 ;
- TEAEs with CTCAE grade ≥ 3 per person-years exposure;
- Related TEAEs with CTCAE grade ≥ 3 per person-years exposure;
- All AEs resulting in death;
- Serious TEAEs;
- Serious TEAEs per person-years exposure;
- All serious TEAEs by decreasing frequency of PT for AG-221;
- Serious TEAEs related to study treatment;
- Serious TEAEs related to study treatment per person-years exposure;
- TEAEs leading to study drug withdrawal;
- TEAEs leading to study drug withdrawal per person-years exposure;
- TEAEs related to study drug and leading to study drug withdrawn;
- TEAEs with leading to dose reduction;
- TEAEs with leading to dose reduction per person-years exposure;
- TEAEs related to study drug and leading to study drug dose reduction;
- TEAEs leading to study drug dose interruption;
- TEAEs leading to study drug dose interruption per person-years exposure;
- TEAEs related to study drug and leading to study drug dose interruption;
- TEAEs leading to study drug dose reduction and dose interruption;
- TEAEs related to study drug and leading to dose reduction and study drug dose interruption;
- TEAEs for the following baseline subgroups (provided when the number of subjects is sufficient):
 - Gender (male and female);
 - Age (≥ 60 years and < 70 years, ≥ 70 years and < 80 years, ≥ 80 years);
 - Region (North America, South America, Europe, Australia, Asia; US vs. Non-US);
 - Baseline ECOG performance status (Grade 0, 1, 2);
 - Prior intensive therapy for AML (yes versus no) (IVRS and CRF source);
 - Primary refractory: yes versus no
 - Prior allogeneic HSCT for AML (yes versus no) (IVRS and CRF source);

- Baseline ANC value ($\leq 0.5 \times 10^9/L$, $0.5 < 1 \times 10^9/L$, $\geq 1 \times 10^9/L$)
- Baseline creatinine clearance value (< 45 , $45 < 60$, ≥ 60 mL/min);
- Best clinical response (CR, PR, SD, PD) adjusted by person years on treatment.

In addition, the impact of dose escalation to AEs will be explored. Sensitivity analyses will be carried out for the following two tables:

- All TEAEs by AG-221 ≤ 100 mg and AG-221 > 100 mg cohorts:
AEs which occurred in subjects which only received doses of AG-221 ≤ 100 mg, and AEs which occurred prior to a dose switching to > 100 mg for subjects which had an escalated dose, or AEs which occurred following a reduction to ≤ 100 mg following an escalation are to be counted in ≤ 100 mg cohort. Only AEs which occurred after a dose > 100 mg was administered and occurred within 28 days following this dose administration, and where there were no subsequent dose reductions between escalated dose date and AE start date will be counted in the > 100 mg cohort.
- TEAEs with CTCAE grade ≥ 3 by AG-221 ≤ 100 mg and AG-221 > 100 mg cohorts.

Listings for the corresponding summary tables will be presented separately. Non-treatment-emergent AEs will also be included in one of the listings.

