All AEs will be recorded by the investigator from the time the subject signs informed consent until 28 days after the last dose of IP or until the EOT visit, whichever is longer, as well as those SAEs made known to the investigator at any time thereafter that are suspected of being related to IP. Adverse events and SAEs will be recorded on the AE page of the eCRF and in the subject's source documents. All SAEs must be reported to Celgene Drug Safety within 24 hours of the investigator's knowledge of the event by facsimile, or other appropriate method, using the SAE Report Form, or approved equivalent form.

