## 1. JUSTIFICATION FOR AMENDMENT

[figure not shown]
Significant changes included in this amendment are summarized below:

- ***Sample size was increased and statistical considerations were updated.***

AG-221 (enasidenib) was approved by the Food and Drug Administration (FDA) in the United States (US) for the treatment of adult patients with relapsed or refractory AML with an isocitrate dehydrogenase 2 (IDH2) mutation as detected by an FDA-approved test. This approval may allow subjects in the conventional care regimen arm to receive commercially available AG-221 (enasidenib), leading to statistical power loss in detecting the treatment effect on overall survival. To remedy this statistical power loss, Study AG-221-AML-004 increased sample size from 280 to 316 subjects and updated statistical considerations (eg, event size was increased from 193 to 250 deaths, etc). (Refer to the Protocol Summary, Section 3.1.1, Figure 1, Section 4.1, and Sections 9.3, 9.6.1, and 9.8.)

- ***Study duration was updated.***

The expected duration of this study was changed from approximately 28 months to 78 months because the enrollment period was extended from 24 months to 42 months to increase the sample size as mentioned above, and to submit the final study report and data set with 3 years of follow-up per the Post Marketing Requirements by the FDA (NDA 209606 APPROVAL 1-Aug-2017 Reference ID: 4132874). Accordingly, the definition of the End of Trial has been updated as either the date of 36 months from the last subject randomized date, or the date when all subjects discontinued from study treatment and no subject is available for survival follow-up, whichever is the later date. (Refer to the Protocol Summary, Table 2, Sections 3.2 and 3.3.)

- ***Fasting (preferred) lipid panel was added at 2 more timepoints.***

Fasting (preferred) lipid panel was added on Day 1 of Cycles 2 and 3 to allow for monitoring lipid changes during early cycles of study treatment. (Refer to Table 3.)

- ***The fasting requirement for lipid panel was updated.***

The most recent European guideline indicates that non-fasting blood samples are sufficient for assessing plasma lipid profiles (Nordestgaard, 2016). Thus, the fasting requirement for lipid panel was updated, particularly for subjects who experience clinically meaningful elevations of lipids, per the investigator's assessment. (Refer to Table 3 and Section 6.2.)

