4. INVESTIGATIONAL PLAN

4.1. Overall Study Design and Plan

This is an international, multicenter, open-label, randomized, Phase 3 study comparing the efficacy and safety of AG-221 versus CCRs in subjects 60 years or older with AML refractory to or relapsed after second- or third-line AML therapy and positive for an IDH2 mutation.

It is planned that approximately 316 subjects will be randomized in a 1:1 ratio to receive either the AG-221 treatment or the CCR treatment option pre-selected by the Investigator prior to randomization. Randomization will be stratified by prior intensive therapy for AML (yes versus no), primary refractory (i.e., morphologic complete remission [CR], CR with incomplete neutrophil recovery [CRi], or CR with incomplete platelet recovery [CRp] has never been attained) (yes versus no), and prior allogeneic hematopoietic stem cell transplantation (HSCT) for AML (yes versus no).

The treatment options in the CCR treatment arm include:

- BSC only: continuous 28-day cycles of BSC. Best supportive care includes, but is not limited to, hydroxyurea for leukocytosis and/or differentiation-like syndrome, anti-infectives, analgesics, antiemetics, antipyretics, transfusions and nutritional support (refer to [protocol Section 8](#) for details);
- Azacitidine SC plus BSC: continuous 28-day cycles of azacitidine 75 mg/m²/day SC for 7 days, plus BSC;
- LDAC SC plus BSC: continuous 28-day cycles of cytarabine 20 mg SC twice a day (BID) for 10 days, plus BSC;
- IDAC IV plus BSC: 28-day cycles of cytarabine 0.5 to 1.5 g/m²/day IV for 3 to 6 days, per standard institutional practice, plus BSC; only BSC given after IDAC therapy concludes per standard institutional practice.

Subjects randomized to the AG-221 treatment arm will receive AG-221 100 mg PO once a day on Days 1 to 28 of each 28-day cycle, plus BSC. Dose escalation to 200 mg may occur for augmenting treatment response.

Study treatment starts within 3 days after randomization. No crossover between any of the treatment options will be permitted during the course of study treatment per protocol.

Dosing interruptions, delays, or dose modifications may occur for managing toxicities and/or augmenting treatment response during study treatment.

[figure not shown]

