5.2.3. Safety Population

The safety population includes all randomized subjects who received at least 1 dose of study treatment. Because BSC only treatment may consist of blood products or antibiotics, etc. administered as needed, subjects who are randomized to the BSC arm option will be included in the safety population if they have had at least 1 safety assessment after randomization. The safety population will be used for all safety analyses and drug exposure. Subjects will be analyzed according to the initial treatment actually received.

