6. SUBJECT DISPOSITION

Subject disposition (analysis population allocation, entered, discontinued, along with primary reason for discontinuation) will be summarized using frequency and percent for both treatment and follow-up phases. Enrollment by country and site will also be summarized.

The disposition of subjects will be summarized with counts and percentages. A summary of subject disposition will be presented by treatment group for the following analysis populations:

- ITT population
- mITT population
- Safety population

A listing of reasons for exclusion from the mITT population will be provided. A separate listing will be provided for subjects who were not randomized (screen failures) with reasons for screening failure.

Reasons for treatment discontinuation will be collected on the case report form (CRF) and will be summarized for all randomized subjects with the following categories:

- Death
- Adverse event
- Pregnancy
- Progressive disease
- Withdrawal by subject
- Non-compliance with study drug
- Lost to follow-up
- Study terminated by Sponsor
- Transition to commercially available treatment
- Physician decision
- Disease relapse
- Protocol violation (to be specified on the eCRF)
- Other (to be specified on the eCRF)
- Other: Hematopoietic Stem Cell Transplantation

Reasons for study discontinuation will be collected on the CRF and will be summarized for all randomized subjects and all subjects who enter the follow-up phase with the following categories:

- Screen failure
- Death
- Adverse event
- Pregnancy
- Progressive disease
- Withdrawal by subject
- Lost to follow up
- Study terminated by sponsor
- Transition to commercially available treatment
- Physician decision
- Disease relapse
- Protocol violation (to be specified on the eCRF)
- Other (to be specified on the eCRF)

Additional summaries will be provided for number of subjects per randomization stratum by randomized treatment group, as well as number of subjects by study site.

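### The adverse-event window for the dosed options does not end at the first subsequent AML therapy, so commercial AG-221 toxicity can be tabulated under CCR; tables cut at that therapy should be added

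*SAP*

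**What the plan says.** - **TEAE definition (SAP 11.1).** Events count from the start of study drug "through 28 days after the last study treatment or until the EOT visit, whichever is longer". Later serious events suspected to be related to the investigational product are added.
- **Safety treatment period (SAP 11).** For AG-221, azacitidine, LDAC and IDAC it is "date of first dose through date of last dose + 28 days, or until the EOT visit, whichever is longer". For the fourth CCR option it differs: "BSC only: date of randomization through date of treatment discontinuation".
- **Collection (Protocol 10.1).** Adverse events are recorded "until 28 days after the last dose of IP or until the EOT visit, whichever is longer".
- **Attribution (SAP 5.2.3).** "Subjects will be analyzed according to the initial treatment actually received".
- **Exposure (SAP 9.1 and 11.1).** Duration of exposure also carries a 28-day tail, shortened only for death or data cut-off. The person-years for TEAE rates run to the end of the TEAE period.
- **Switching is foreseen.** Of the US approval, the protocol's amendment justification says "This approval may allow subjects in the conventional care regimen arm to receive commercially available AG-221 (enasidenib". It gives this as the reason for raising the sample size from 280 to 316 subjects and the events from 193 to 250 deaths. SAP 6 lists "Transition to commercially available treatment" among the reasons for stopping treatment. Protocol 8.2 requires study treatment to stop if other AML therapy is needed.
- **Elsewhere, subsequent therapy is handled.** SAP 10.3.1.2 censors EFS at new anti-cancer therapy. SAP 10.2 lists OS sensitivity analyses for subsequent AML therapy and off-protocol AG-221. Protocol 6.3 ends late transfusion collection at the first subsequent AML therapy.

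**The concern.** No safety table separates time on study treatment from time on the next AML therapy. For a CCR subject who moves to commercial AG-221, that next therapy is the test drug. Its characteristic toxicities would then appear in the control column, although no CCR option contains an IDH inhibitor.

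The differentiation-syndrome analysis in SAP 11.2 is the most exposed. It takes any investigator-reported event that qualifies as a TEAE and measures onset from the start of treatment. For a switched subject that is the start of the CCR regimen, not the start of AG-221. SAP 11.1 already sorts AG-221 events by the dose level at onset, so the plan accepts time-dependent attribution within one arm but does not apply it here.

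The amount of next-line time inside the window also depends on the dosing schedule. AG-221 is given daily, so its last dose falls close to the decision to stop. The cycled comparators may have been off drug for up to three and a half weeks by then. Comparative safety is a stated secondary objective (SAP 3.2), and both effects bear on it.

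**Working it through.** **Step 1: dosing days.** AG-221 is given as "AG-221 100 mg PO once a day on Days 1 to 28 of each 28-day cycle" (SAP 4.1), which is 28 of 28 days. SAP 9.4 and Protocol 3.1.1 give 10 days for LDAC, 7 for azacitidine and 3 to 6 for IDAC. The planned dose intensities in SAP 9.4 confirm the first two:

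- LDAC: 20 mg × 2 × 10 / 28 = 14.29 mg/day (stated 14.3).
- Azacitidine: 75 × 7 / 28 = 18.75 mg/m²/day (stated 18.75).

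**Step 2: formula.** Let d be the cycle day on which the decision to stop is made, k the last dosing day of the cycle, and g the gap in days before the next therapy. The last dose falls on min(d, k), and the window runs 28 days beyond it. Days of next-line therapy inside the window = max(0, min(d, k) + 28 − d − g).

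For d = 28 and g = 0 this equals k. For d uniform on 1 to 28 and g = 0 the mean is 28 − (28 − k)(29 − k)/56:

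- Azacitidine: 28 − 21 × 22/56 = 19.75
- LDAC: 28 − 18 × 19/56 = 21.89
- IDAC: 28 − 25 × 26/56 = 16.39 (3 days) to 28 − 22 × 23/56 = 18.96 (6 days)

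**Step 3: results, in days per switching subject.** The documents give neither d nor g, so both are assumptions and are varied. Fourteen days is the pre-study washout in Protocol 4.3, used here only as a reference gap.

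| Stop and gap | AG-221 | Azacitidine | LDAC | IDAC |
|---|---|---|---|---|
| Cycle end, 0 days | 28 | 7 | 10 | 3–6 |
| Days 22–28 (mean), 0 days | 28 | 10 | 13 | 6–9 |
| Uniform, 0 days | 28 | 19.8 | 21.9 | 16.4–19.0 |
| Cycle end, 7 days | 21 | 0 | 3 | 0 |
| Uniform, 7 days | 21 | 12.8 | 14.9 | 9.8–12.0 |
| Cycle end, 14 days | 14 | 0 | 0 | 0 |
| Uniform, 14 days | 14 | 6.8 | 8.3 | 4.8–6.3 |

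Scheduled marrows fall within 7 days before Day 1 of the next cycle (Protocol Table 3), which pulls stops for assessed progression towards cycle end. Stops for toxicity or rapid change can fall on any day. An EOT visit 7 days after the decision (Protocol 6.2.3 allows ±7 days) raises the IDAC cycle-end figure from 3–6 to 7 and changes little else.

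**Step 4: from subject to arm.** Next-line time in an arm = share of the arm that switches × overlap per switcher. With no gap, the two arms are equal when the CCR share exceeds the AG-221 share by the factor 28/overlap:

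- Cycle end: 28/10 = 2.8 to 28/3 = 9.3.
- Uniform: 28/21.9 = 1.3 to 28/16.4 = 1.7.

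Neither share is given.

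**Step 5: what a cut would remove.** With a cycle-end stop and an immediate switch, ending the window at the next therapy leaves 28 − overlap days of post-dose observation: 0 for AG-221, 21 for azacitidine, 18 for LDAC and 22–25 for IDAC.

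**Step 6: BSC only.** SAP 11 ends the safety period at treatment discontinuation, so the overlap is 0. SAP 11.1 states one 28-day or EOT rule with no exception for BSC only. The two sections disagree.

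**The case against.** The present window has real merits. It matches what the protocol collects, and it gives every dosed subject the same minimum of 28 days after the last dose. Cutting it in the main tables would let investigator-chosen switch timing set the length of follow-up in an open-label trial. Step 5 shows that it would take post-dose observation mainly from AG-221, where late toxicity needs to be seen. This stands, and it is why the main window should not be replaced.

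The plan also gives some protection. Related, related grade 3 or higher, related serious and related special-interest tables are planned. Safety is shown by CCR option. Adverse events and subsequent systemic AML therapies are listed, so an individual case could be traced. The person-years take in the same time as the events. These points reduce the problem but leave the all-causality and special-interest summaries unchanged.

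Three stronger readings are tempting, and the documents do not support them:

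- **A reader might infer that AG-221 absorbs far more next-line toxicity than the comparators.** The contrast of 28 against 3 to 10 days needs every stop at cycle end and an immediate switch. With uniform stopping the ratio per switcher is only 1.3 to 1.7, and more frequent switching in CCR could cancel it.
- **A reader might infer that all CCR subjects are affected.** Under SAP 11, BSC-only subjects have no 28-day tail. They would be affected only if SAP 11.1 governs.
- **A reader might take the discontinuation reason in SAP 6 as evidence of CCR switching.** It applies to all randomized subjects, so AG-221 subjects who move to commercial supply fall there too. The approval cited is US only, in an international trial whose US share is not given.

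**Conclusion.** The gap is in the text. For AG-221, azacitidine, LDAC and IDAC, neither the TEAE window nor the safety period ends at a subsequent AML therapy, and events stay with the initial treatment. Commercial AG-221 toxicity that arises within 28 days of the last azacitidine, LDAC or IDAC dose, or by the EOT visit if later, is therefore counted under CCR in every table not filtered by causality.

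Per switching subject, the overlap is longer for AG-221 than for each cycled comparator in every scenario tested. With no gap the ratio runs from about 1.3 to 9. With a gap and cycle-end stops, the comparator overlap can fall to zero. These figures assume that dosing starts on Day 1 of the cycle, and they use the stated stop days and gaps. Azacitidine weekend skipping (Protocol 7.2.2) could move its last dose to Day 9 and add 2 days.

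The documents do not allow an arm-level difference or a number of misattributed events to be stated, since they give no switching share, no time to next therapy and no event rate on commercial AG-221. The primary OS inference is not touched. The case is for added tables, not for a new main window.

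**What to change.** 1. Keep the present window for the main safety tables.
2. Add prespecified tables for all TEAEs, grade 3 or higher, serious and special-interest TEAEs, and laboratory abnormalities, ending the day before the first subsequent AML therapy. For CCR subjects this includes commercial AG-221. AG-221 subjects who move to commercial AG-221 are not cut at that move.
3. Cut the person-years in those tables at the same date.
4. Flag differentiation-syndrome and other special-interest events in CCR subjects that start after off-protocol AG-221.
5. Reconcile the BSC-only window between SAP 11 and SAP 11.1, and state one rule.

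The cost is SAP wording, one derived date and a few extra tables. Subsequent-therapy data are already collected (Protocol 6.3), and the start date is already needed for EFS censoring (SAP 10.3.1.2). The added tables will hold slightly fewer events and less exposure time. They will also have shorter post-dose observation, mainly for AG-221, and a footnote should say so.

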9.1. Duration of Treatment Exposure and Duration of Treatment

Duration of treatment exposure and duration of treatment will be summarized by treatment group.

Duration of treatment exposure (days) is defined as: Treatment end date – treatment start date + 28 days. The treatment start date is the date of the first dose of study drug, and the treatment end date is the last dose date. If death date or data cut-off is earlier than 28 days after treatment end date, duration of treatment exposure is defined as: the earlier of death date and data cut-off – treatment start date + 1. Duration of treatment exposure will be summarized by treatment group of AG-221, azacitidine, LDAC, and IDAC. For BSC only group, duration of treatment exposure is the same as duration of treatment defined below.

For AG-221, azacitidine, LDAC, and IDAC groups, duration of treatment (days) is defined as: Treatment end date – treatment start date + 1. For subjects who are still on treatment at a data cut-off date, treatment end date will be the earlier date of data cut-off and the last dose date.

For BSC only group, duration of treatment is defined as the period from date of randomization through the date of discontinuation from the treatment period, date of death, or clinical data cut-off date, whichever is earliest (calculated as the earliest of death, clinical data cut-off, or discontinuation date – randomization date + 1). Duration of treatment will be summarized for all treatment groups including the BSC only group.

See Section 5 for cycle length and cycle number calculations. Average cycle length (days), average number of days dosed per cycle, and number of treatment cycles will be summarized by treatment group. Average cycle length and average number of days dosed per cycle will not be summarized for BSC only group. The number of days dosed per cycle is defined as the number of days with a non-missing dosing date within that cycle. For average cycle length and average number of days dosed per cycle, a single average value will be computed for each subject first and then the descriptive statistics will be computed for each treatment group. Additionally, the count and percent of subjects by number of cycles of treatment will be provided for each treatment group.

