9.6. Dose Modification

This part does not apply to BSC only group.

The number of subjects who have at least one dose modification, number of dose modifications per subject, and reasons for dose modifications will be summarized by treatment group. Details of dose adjustments will be provided in a by subject listing.

According to protocol, under specific circumstances, AG-221 dose may increase for augmenting treatment responses. Number of subjects who undergo dose escalation, number of subjects who have dose modification after dose escalation will be summarized. Reasons for dose modifications after dose escalations will also be summarized.

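### Rates of TEAEs leading to dose reduction or interruption count BSC-only time in the CCR Overall denominator, and post-dose time in every study-drug column

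*SAP*

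**What the plan says.** SAP 11.1 lists "TEAEs with leading to dose reduction per person-years exposure" and "TEAEs leading to study drug dose interruption per person-years exposure" among the TEAE tables. Neither entry defines its own person-time. The one definition in that section is attached to the all-TEAE rate table and counts "overall treatment exposure (days) from first dose date (or randomization date for BSC only group) to the end of the TEAE period", divided by 365.25.

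For the drug groups, SAP 11 sets the safety period as "date of first dose through date of last dose + 28 days, or until the EOT visit, whichever is longer". SAP 9.1 has a second definition of exposure, "Treatment end date – treatment start date + 28 days", shortened by a rule that begins "If death date or data cut-off is earlier than 28 days after treatment end date". BSC-only person-time runs from randomization to discontinuation of the treatment period, death or data cut-off, with no 28-day addition.

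Safety tables are shown for AG-221, CCR Overall and each CCR option (SAP 11). On dose modification, SAP 9.6 states: "This part does not apply to BSC only group". SAP 11.1 does not repeat that exclusion.

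**The concern.** A rate per person-year should divide events by time in which the event could occur. Two parts of this denominator fail that test.

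- **BSC-only time.** These subjects have no study drug whose dose can be reduced or interrupted. They add person-years to CCR Overall and no events.
- **Time after the last possible dose change.** For AG-221, dosed on every day of the cycle, the added period lies beyond the final dose of a completed last cycle.

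Exposure-adjusted rates are meant to make AG-221 and CCR tolerability comparable when treatment lengths differ. Here the adjustment brings in a distortion that depends on treatment length and on how many CCR subjects were assigned to BSC only.

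**Working it through.** The plan states no rate or person-year total for these tables, so there is no figure of its own to reproduce.

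**Inputs**
- Drug-group exposure: last dose − first dose + 28 days (SAP 9.1). Duration of treatment: last dose − first dose + 1. The difference is 27 days.
- Dosing days n in each 28-day cycle: AG-221 28, azacitidine 7, LDAC 10, IDAC 3 to 6 (SAP 4.1).
- Assumed: the number of cycles k, and the BSC-only share b of CCR person-years. The documents give neither. Protocol 7.2.1 sets only an aim of at least 6 AG-221 cycles.

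**Step 1: BSC-only time.** With e events, drug-option time T and BSC-only time B, the reported rate is e/(T + B) and the rate among subjects with a dose to modify is e/T. Their ratio is T/(T + B) = 1 − b.
- b = 10%: 0.90
- b = 20%: 0.80
- b = 30%: 0.70

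Only the CCR Overall rate is lowered this way. The AG-221 and drug-specific CCR columns contain no BSC-only time, and the BSC-only column is an uninformative zero.

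**Step 2: AG-221 tail.** At-risk days are 28k and denominator days are 28k + 27.
- k = 6: 168/195 = 0.86
- k = 4: 112/139 = 0.81
- k = 2: 56/83 = 0.67

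**Step 3: comparator tail.** The last dose falls on day n of the final cycle and the denominator ends on day n + 27, which is n − 1 days past day 28. That is 6 days for azacitidine, 9 for LDAC, 2 to 5 for IDAC and 27 for AG-221. Counting the whole last cycle as at risk, the ratio is 28k/(28(k − 1) + n + 27). For 2 cycles:
- azacitidine: 56/62 = 0.90
- LDAC: 56/65 = 0.86
- IDAC (6 days): 56/61 = 0.92

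**Step 4: between arms, with equal true rates.** AG-221 for 6 cycles against 2 comparator cycles gives an apparent rate ratio of 0.862/0.903 = 0.95 for azacitidine and 0.862/0.862 = 1.00 for LDAC. Adding BSC-only time to a CCR Overall column otherwise made up of azacitidine for 2 cycles:

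| AG-221 cycles | b | Apparent AG-221/CCR ratio |
|---|---|---|
| 6 | 10% | 0.862/(0.903 × 0.90) = 1.06 |
| 6 | 20% | 0.862/(0.903 × 0.80) = 1.19 |
| 6 | 30% | 0.862/(0.903 × 0.70) = 1.36 |
| 2 | 20% | 0.675/(0.903 × 0.80) = 0.93 |

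At 6 AG-221 cycles the two effects cancel at b = 1 − 0.862/0.903, about 4.6%.

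**The case against.** A reader might infer something stronger: that no dose can be changed at any time after the last dose, so short comparator treatment is diluted most and AG-221 is made to look worse. On first-to-last-dose time, azacitidine for 2 cycles would have 35/62 = 0.56, and against AG-221 for 6 cycles the apparent ratio would be (168/195)/(35/62) = 1.53. The documents do not support this. After azacitidine, low counts postpone the next cycle, and its dose can depend on how long recovery takes (Protocol 7.2.2.1). The next LDAC cycle may be put back by as much as 2 weeks (7.2.3). IDAC requires recovery before each cycle (7.2.4). The drug-free days are therefore time at risk, and counting them turns 1.53 into 0.95. Ending person-time at last dose would leave 7 days for one azacitidine cycle and over-correct.

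Other points also have force. An AG-221 cycle can start late because of toxicity (7.2.1.4), and SAP 9.1 cuts the tail at death or data cut-off, so the Step 2 figures show the full dilution on that definition. Under SAP 11 a later EOT visit lengthens the tail instead. The person-year definition in SAP 11.1 carries a footnote marker whose text is absent from the copy reviewed, and it may qualify the end of the period. Separate option columns and the versions of both tables without person-years limit the harm, and a common denominator keeps the rate tables comparable with one another.

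None of this answers the BSC-only point. SAP 9.6 excludes that group from dose-modification summaries, and the two rate tables do not.

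**Conclusion.** The point holds in two parts of unequal strength.

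1. **BSC-only time in CCR Overall.** The rate is understated by exactly the BSC-only share of CCR person-years. The result is algebraic; only the size of the share, illustrated at 10% to 30%, is assumed.
2. **Post-dose tail.** AG-221 rates are diluted to about 0.86 of the at-risk rate at 6 cycles and 0.67 at 2, with assumed cycle counts and no cut at death or data cut-off. The comparator drugs lose less when the last cycle counts as at risk: 0.86 to 0.92 at 2 cycles.

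The net direction between arms is not established. The apparent ratio runs from 0.93 to 1.36 over the illustrated cases and depends on treatment lengths and a BSC-only share that the documents do not give. The finding is about two descriptive safety tables. No endpoint, test or decision rule is touched.

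**What to change.** For the dose-reduction and dose-interruption rate tables only:

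- Exclude BSC-only subjects from both the numerator and the denominator of CCR Overall, and label the column 'CCR, active drug options'. This follows SAP 9.6.
- End person-time at the end of the last treatment cycle instead of the end of the TEAE period, cut at death or data cut-off. The SAP should state that the last cycle ends 28 days after it starts, counting the start day; SAP 15.1.2 already treats a cycle as 28 days.
- Use first-to-last-dose time at most as a sensitivity bound.
- State this denominator beside the two table entries in SAP 11.1, so that it is clear neither general definition (SAP 9.1 or 11.1) applies to them.

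The cost is a few lines of SAP text and two table specifications, with no new data. The small downside is that CCR Overall in these two tables no longer covers the whole CCR safety population, which the new label makes plain.
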